8. SELECTION AND ENROLLMENT OF SUBJECTS

8.1. Inclusion Criteria and Exclusion Criteria

8.1.1. Inclusion Criteria:

Subjects meeting all of the following criteria may be included in the study:

1. Male or female subjects between 18-80 years of age, inclusive
2. Subjects with a diagnosis of probable or definite ALS in accordance with the Revisited El-Escorial Criteria ([Cedarbaum, 1999](#))
3. Subjects must be currently on an oral diet and able to take foods and liquids by mouth equivalent to a score of 3 or above on the Functional Oral Intake Scale ([Crary, 2005](#)).
4. Subjects with no known allergy to barium, riluzole or inactive ingredients* in ROSF
5. Subjects or subject's legally authorized representative must be willing and able to give informed consent/assent and HIPAA authorization.
6. Subjects must have the ability to comprehend and be informed of the nature of the study, as assessed by the PI or Sub-Investigator.
7. Subjects prescribed riluzole at or before the dose of study drug. (The study is open to subjects currently taking riluzole at screening, subjects who are not currently taking riluzole at screening who have taken riluzole in the past, and subjects to be newly started on riluzole (given as ROSF in this study.)
8. Female subjects of childbearing potential must have a negative urine pregnancy test at Screening and Visit 1. Female subjects of childbearing potential (i.e. not surgically sterile, not 2 years postmenopausal, or not with a sterile partner) must have a negative pregnancy test at screening and Visit 1, agree to abstinence, be practicing double barrier contraception or using an FDA approved contraceptive (e.g., licensed hormonal or barrier methods) for greater than 2 months prior to screening visit and commit to an acceptable form of birth control for the duration of the study and for 30 days after participation in the study
9. Availability to volunteer for the entire study duration and willing to adhere to all protocol requirements

*See Investigator Brochure

8.1.2. Exclusion Criteria:

Potential subjects meeting any of the following criteria will be excluded:

1. Subjects who score 2 or below on the Functional Oral Intake Scale ([Crary, 2005](#))

CONFIDENTIAL INFORMATION

The information in this study protocol is confidential. Any disclosure, copying or distribution of the information contained within is strictly prohibited without written consent from MonoSol Rx LLC.

2. Subjects with a prior swallowing study that has shown a PAS of 3 or greater
3. Subjects with a history of two or more episodes of aspiration pneumonia requiring hospitalization
4. Subjects with a history of clinically significant liver disease, renal disease, or any other medical condition judged to be exclusionary by the investigator
5. Subjects who are unwilling to sign informed consent or subjects who for any other reason in the judgment of investigator are unable to complete the study
6. Female subjects who have a positive urine pregnancy test (β hCG) at screening or Visit 1, are trying to become pregnant or are breastfeeding.
7. Subjects with active cancer within the previous 2 years, except treated basal cell carcinoma of the skin
8. Subjects who have taken any experimental drug within 30 days prior to enrollment or within 5 half-lives of the investigational drug –whichever is the longer period. However, subjects who have previously completed other MonoSol Rx sponsored ROSF clinical studies within the last 30 days prior to enrollment may be eligible for consideration for entry into this study.
9. Subjects with moderate or severe renal impairment as defined by a calculated creatinine clearance of ≤ 50 mL/minute
10. Subjects currently taking riluzole with ALT levels greater than 5 times upper limit of normal or with evidence of clinical jaundice. (Riluzole should be discontinued in these patients.)
11. Subjects who will be receiving riluzole for the first time who exhibit baseline elevations of several LFTs (especially elevated bilirubin). (These findings at baseline should preclude the use of riluzole including ROSF).
12. Use of potentially hepatotoxic drugs: (e.g., allopurinol, methyldopa, sulfasalazine).
13. Subjects with clinically significant abnormal laboratory values in the judgment of the investigator
14. Use of strong or moderate CYP1A2 inhibitors (e.g., ciprofloxacin, enoxacin, fluvoxamine, methoxsalen, mexiletine, thiabendazole, vemurafenib, zileuton) and CYP1A2 inducers (e.g. rifampin and barbiturates) in the previous 30 days before first drug administration.
15. Anything else that, in the opinion of the investigator, would place the subject at increased risk or preclude the subject's full compliance with or completion of the study

CONFIDENTIAL INFORMATION

The information in this study protocol is confidential. Any disclosure, copying or distribution of the information contained within is strictly prohibited without written consent from MonoSol Rx LLC.

16. Employee or immediate relative of an employee of the investigator, MonoSol Rx LLC, any of its affiliates or partners, or inVentiv Health.

8.2. Subject Withdrawal

Inclusion in the study is entirely voluntary and subjects may withdraw at any time for any reason. Possible reasons for withdrawal are serious adverse events, adverse events, and subject's choice. Subjects who elect to withdraw from the study after taking study medication but prior to completion of the VFSS 2-PAS will be asked to comply with end of study clinical laboratory evaluation(s). For a complete list of all tests to be performed, see [Section 10.3.7, Laboratory Evaluations](#). Subjects who withdraw due to an adverse event will be followed whenever possible until resolution of the adverse event. It may be appropriate for the subject to return to the site 2 weeks after the subject is off study to evaluate for resolution of any adverse events and to receive further information about options for future clinical care. The Investigator will decide the course of action.

8.3. Study Enrollment Procedures

The following screen procedures will be conducted on each potential subject:

- Obtain informed consent as evidenced by subject or subject's legally authorized representative signing an informed consent. Informed consent will be signed prior to any study-related procedures and prior to screening per protocol. Informed consent will be obtained by the site PI and/or his or her designee.
- Record medical history
- Documentation of disease
- Obtain vital signs (temperature, respiratory rate (RR), heart rate (HR), blood pressure (BP), height and weight
- Collect blood and urine for baseline clinical laboratory evaluation(s) and urine pregnancy test (females of childbearing potential only). For a complete list of all tests to be performed, see [Section 10.3.7, Laboratory Evaluations](#).
- Complete physical and neurological examinations
- ALS Functional Rating Scale-Revised (ALSFRS-R)
- Eating Assessment Tool-10 (EAT-10)
- Functional Oral Intake Scale (FOIS)
- Collection of pretreatment AEs, if subject receiving riluzole pre study
- Principal Investigator's/Sub-Investigator's review of Inclusion/Exclusion criteria and all screening results/data to assess eligibility of each potential subject

CONFIDENTIAL INFORMATION

The information in this study protocol is confidential. Any disclosure, copying or distribution of the information contained within is strictly prohibited without written consent from MonoSol Rx LLC.

- Record/Review concomitant medications

Screening procedures will be completed within 28 days of Visit 1.

8.3.1. Subject Recruitment and Retention

Participants will be recruited from patients followed in the neuromuscular programs at The University of Florida. Potential participants will be contacted by the investigators or their staff and invited to participate. These recruitment strategies will include a mechanism by which the subjects can provide their contact information.

8.3.2. Screening Logs

Screening logs to document reasons for ineligibility and reasons for nonparticipation of eligible subjects will be maintained to document number of subjects referred, referral source, number screened, number failed due to ineligibility or nonparticipation of eligible subjects, and reasons for ineligibility or nonparticipation of eligible subjects.

8.3.3. Randomization/Treatment Assignment

Randomization is not applicable. This is an open label swallowing safety and tolerability trial.

CONFIDENTIAL INFORMATION

The information in this study protocol is confidential. Any disclosure, copying or distribution of the information contained within is strictly prohibited without written consent from MonoSol Rx LLC.

9. DRUG PRODUCT

9.1. Drug Information

Table 2 Drug Information

Treatment	
Drug Name	Riluzole
Strength	50mg
Dosage Form	Oral Soluble Film
Manufacturer	MonoSol Rx LLC
Dose	1 x 50mg

9.2. Handling of Study Drug, Packaging and Labeling

The Sponsor will supply a sufficient quantity of the study drug to allow completion of this study including some excess for replacement if needed. The study drug will be sent to the Investigator packed in individual unit-dose packages. Each unit-dose package will be labeled in English containing at minimum: Protocol Number, Drug Name, Strength, Route of Administration, and statements “Caution: New Drug – Limited by United States Law to Investigational Use Only”, “Keep Out of Reach of Children”, storage conditions and batch/lot number. The site pharmacies will keep a log of study drug kits received and dispensed identified by subject ID, subject initials, and date dispensed. Study drug will be stored at room temperature in a double-locked room or on-site pharmacy as directed by institutional SOP. The site pharmacist or coordinator as indicated in the delegation log will dispense study drug at the study visit. This is a single dose study. The dose of study drug will not be adjusted.

In accordance with local regulatory requirements, the investigator, designated site staff, or head of the medical institution (where applicable) must document the quantity of investigational product administered to study subjects, the quantity received, and the quantity destroyed upon completion of the study. The investigator is responsible for ensuring product accountability records are maintained throughout the course of the study. The inventory record will include details of MonoSol Rx study drug received and dispensed to subjects, batch, and ID numbers will be maintained by the Investigator.

At the completion of the study, all unused study drug, including any excess, will be retained by the Investigator until the authorization to return or destroy is received from the Sponsor. An accounting must be made of any drug deliberately or accidentally destroyed.

CONFIDENTIAL INFORMATION

The information in this study protocol is confidential. Any disclosure, copying or distribution of the information contained within is strictly prohibited without written consent from MonoSol Rx LLC.

9.3. Concomitant Interventions

All concomitant medications received by a subject during participation in the study will be recorded on the appropriate source documents.

9.3.1. Required Concomitant Medications/Interventions

No concomitant medications or interventions are required per protocol.

The study is open to subjects currently taking riluzole at screening, subjects who are not currently taking riluzole at screening who have taken riluzole in the past, and subjects to be newly started on riluzole (given as ROSF at the start of this study.)

9.3.2. Prohibited Medications/Interventions

Concomitant medications and interventions will be reviewed at screening and Visit 1. The investigator may choose to exclude a subject from participation if a concomitant medication or intervention is judged likely to interfere with the study objectives or to affect the subject's safety.

The following drugs are known to interact with riluzole (Rilutek® tablets US Package Insert; revision 04/2016) and should not be administered with ROSF:

- Agents that may increase riluzole blood concentration; Strong or moderate CYP1A2 inhibitors (e.g., ciprofloxacin, enoxacin, fluvoxamine, methoxsalen, mexiletine, thiabendazole, vemurafenib, zileuton).
- Agents that may decrease riluzole plasma concentrations: CYP1A2 inducers (e.g. rifampin and barbiturates)
- Potentially hepatotoxic drugs: (e.g., allopurinol, methyl dopa, sulfasalazine)

CONFIDENTIAL INFORMATION

The information in this study protocol is confidential. Any disclosure, copying or distribution of the information contained within is strictly prohibited without written consent from MonoSol Rx LLC.

10. STUDY PROCEDURES

10.1. Schedule of Activities

The schedule of study activities is presented in [Table 3](#).

Table 3 Schedule of Activities

Evaluation	Screening	Visit 1
Written Informed Consent	X	
Inclusion/Exclusion Review	X	X ^a
Documentation of Disease	X	
Record/Review Concomitant Medications	X	X ^a
Medical History/ Demographics	X	
Height and Weight	X	
Vital Signs – HR, BP, RR		X ^b
Vital Signs – HR, BP, RR and temperature	X	X ^a
Comprehensive Physical Exam	X	
Brief Physical Exam		X ^b
Neurological Examination	X	
Brief Neurological Exam		X ^b
Eating Assessment Tool-10 (EAT-10)	X	X ^a
Functional Oral Intake Scale (FOIS)	X	X ^a
ALS Functional Rating Scale - Revised (ALSFRS-R)	X	X ^a
Oral Examination	X	X ^c
VFSS 1 - Penetration-Aspiration Scale (pre-dose)		X
VFSS 2 - Penetration-Aspiration Scale (post-dose)		X
Clinical laboratory evaluation(s)hematology, chemistry, urinalysis) ^d	X	X ^b
Urine Pregnancy Test (females of childbearing potential)	X	X ^a
Adverse Event	X	X ^c
Dispense Study Drug (one dose)		X

^aBefore VFSS 1 procedure

^bAfter VFSS 2 procedure

^cBoth – before VFSS 1 procedure and after VFSS 2 procedure

^dSee [Section 10.3.7 Laboratory Evaluations](#)

CONFIDENTIAL INFORMATION

The information in this study protocol is confidential. Any disclosure, copying or distribution of the information contained within is strictly prohibited without written consent from MonoSol Rx LLC.

10.2. Timing of Study Activities

No study procedures will be performed prior to the signing of the Informed Consent Form (ICF). All subjects will sign an ICF prior to undergoing any study tests or procedures.

Visit 1 should occur within 28 days of the Screening Visit.

Inclusion in the study is entirely voluntary and subjects may withdraw at any time for any reason. Possible reason for withdrawal could include serious adverse events, adverse events, and subject's choice. Subjects who elect to discontinue medication will be asked to comply with end of study clinical laboratory evaluation(s) and urine pregnancy test (females of childbearing potential). For a complete list of all clinical laboratory evaluation(s) to be performed, see [Section 10.3.7, Laboratory Evaluations](#). Subjects who withdraw due to an adverse event will be followed whenever possible until resolution of the adverse event. It may be appropriate for the subject to return to the site 2 weeks after the subject is off study to evaluate for resolution of any adverse events and to receive further information about options for future clinical care. The Investigator will decide the course of action.

10.2.1. Screening procedures

At the screening visit, potential subjects will be informed about study procedures and will then sign an informed consent form. Inclusion/exclusion criteria will be reviewed and a medical history and full physical examination completed. Vital signs, weight, height and concomitant medications will be recorded. Clinical laboratory tests will be performed including complete blood count (CBC) with differential, electrolytes, BUN, creatinine, ALT, AST, total bilirubin, albumin, and a pregnancy test for women of childbearing potential.

The following procedures will be performed during the screening visit:

- Informed consent
- Inclusion/exclusion assessment
- Documentation of Disease
- Medical history
- Record concomitant medications
- Clinical laboratory evaluation(s) see [Section 10.3.7 Laboratory Evaluations](#)
- Urine pregnancy test (females of childbearing potential)
- Height and weight
- Vital signs (including temperature)
- Comprehensive physical and neurological examinations including oral examination

CONFIDENTIAL INFORMATION

The information in this study protocol is confidential. Any disclosure, copying or distribution of the information contained within is strictly prohibited without written consent from MonoSol Rx LLC.

- ALS Functional Rating Scale-Revised (ALSFRS-R)
- Eating Assessment Tool-10 (EAT-10)
- Functional Oral Intake Scale (FOIS)
- Adverse event review, if subject is currently on riluzole

All inclusion and exclusion criteria and clinical laboratory tests will be reviewed by the investigator prior to scheduling the baseline visit (; *Schedule of Activities; Visit 1*). A log will be kept at the site to record all subjects screened for entry into the study. This information will also be captured electronically in the electronic data capture system (EDC). Demographic characteristics of all subjects who are screened will be recorded whether or not they qualify for entry into the study. The reason for non-qualification will be recorded for all subjects who are not eligible. The reason for nonparticipation will also be recorded for subjects who are eligible but choose not to participate in the trial. If a subject fails screening for the study, the subject can be re-screened if the investigator determines it is appropriate to do so. At any time during the study, repeat laboratory tests may be obtained if the investigator or central laboratory believes that a laboratory test result is in error. Additional laboratory tests may also be obtained at any time during the study, at the discretion of the investigator.

10.2.2. On-Study/On-Intervention Evaluations/Procedures

10.2.2.1. Baseline (Day 0, Visit 1):

The baseline visit (Day 0, Visit 1) will include a single dose of study drug. It will be scheduled within 28 days after the screening visit. At this visit, inclusion/exclusion criteria and concomitant medications will be reviewed. Vital signs, brief physical and neurologic examination, as well as study questionnaires and testing will be performed as noted in [Table-3; Schedule of Activities](#).

The following documentation and procedures will be performed at Day 0 (Visit 1):

- Adverse event review (before VFSS 1 procedure and after VFSS2 procedure)
- Inclusion/exclusion assessment (before VFSS 1 procedure)
- Concomitant medications (before VFSS 1 procedure)
- Urine pregnancy test for females of childbearing potential (before VFSS 1 procedure)
- Vital signs HR, BP, RR and temperature (before VFSS 1 procedure)
- Vital Signs HR, BP, RR (after VFSS 2 procedure)
- Oral Exam (before VFSS 1 procedure and after VFSS 2 procedure)
- Videofluoroscopy Swallow Study 1 (VFSS 1; pre dose procedure)
- Administer study drug (one dose)
- Videofluoroscopy Swallow Study 2 (VFSS 2; post dose procedure)

CONFIDENTIAL INFORMATION

The information in this study protocol is confidential. Any disclosure, copying or distribution of the information contained within is strictly prohibited without written consent from MonoSol Rx LLC.

- Brief physical exam (after VFSS 2 procedure)
- Brief neurologic exam (after VFSS 2 procedure)
- Clinical laboratory evaluation(s) see [Section 10.3.7 Laboratory Evaluations \(after VFSS 2 procedure\)](#)

Videofluoroscopy Swallow Study (VFSS 1-PAS)

Subjects will undergo a standardized videofluoroscopic swallowing study (VFSS) for direct visualization of the swallowing process and any episodes of penetration or aspiration. The VFSS represents the gold standard swallowing exam to directly visualize swallowing and specifically aspiration during swallowing. After consent has been verified and screens completed, the patient will be seated and will complete a standardized bolus protocol that includes 12 bolus trial presentations in the following order:

1. 5ml thin liquid barium
2. 5ml thin liquid barium
3. 5ml thin liquid barium
4. Regular sip of thin liquid taken from a cup containing 60cc of thin liquid.
5. Consecutive cup sips of remaining thin liquid barium
6. Tablespoon of thin honey consistency barium
7. Tablespoon of thin honey consistency barium
8. Tablespoon of thin honey consistency barium
9. Tablespoon of pudding consistency barium.
10. Tablespoon of pudding consistency barium.
11. Graham cracker with pudding-thick barium.
12. 13 mm barium tablet (EZ-Disk) with water.

A standard ‘bail out’ criteria used on all VFSS protocols in the Swallowing Systems Core laboratory will be utilized in this study. This represents a standard provision to avoid unnecessary risk to research subjects during VFSS exams and will include cessation of bolus presentations during a specific VFSS test (i.e. either VFSS 1 or VFSS 2) on the third episode of frank aspiration (material entering the airway below the level of the true vocal folds) or residue greater than 75% of either vallecular or pyriform housing that is unable to be cleared by the patient with prompting and strategies. The potential for this to occur is factored into the targeted enrollment of approximately 30 subjects in an effort to complete 25 subjects for the swallowing evaluation consistent with the sample size estimation ([Section 13.5.3; Power](#)).

The start time and finish time for the standardized bolus protocol will be recorded for both VFSS 1 and VFSS 2.

CONFIDENTIAL INFORMATION

The information in this study protocol is confidential. Any disclosure, copying or distribution of the information contained within is strictly prohibited without written consent from MonoSol Rx LLC.

Immediately following VFSS 1-PAS, the patient will then be administered ROSF on the dorsum of tongue along the median lingual sulcus, and the time of administration will be recorded ([Appendix B](#)). Following a three-minute time interval the investigator will confirm that the ROSF has dissolved and VFSS 2-PAS will be performed. If ROSF is not fully dissolved at 3 minutes, start of the second VFSS 2-PAS bolus protocol will be delayed until investigator confirms that ROSF is fully dissolved. The investigator should record whether or not ROSF is fully dissolved at 3 minutes after dosing. In the event that ROSF is not fully dissolved at 3 minutes, the investigator will record the time that it is confirmed that ROSF is fully dissolved.

Videofluoroscopy Swallow Study Test 2-PAS (VFSS 2-PAS)

The identical VFSS standardized bolus protocol exam will be performed provided that the subject did not demonstrate frank, gross and observable silent aspiration during VFSS 1-PAS and provided that the subject's PAS score in baseline test is 7 or below. VFSS will be performed using a Phillips BV Endura fluoroscopic C-arm unit (GE OEC 8800 Digital Mobile C-Arm system type 718074) that is housed within the PI's laboratory and used exclusively for research purposes. Fluoroscopic data will be captured in high resolution at 30 frames per second and in the lateral field of view using a TIMS Dicom (Version 3.2, TIMS Medical, TM, Chelmsford, MA).

The identical standard patient safety bail out criterion will be enforced in VFSS 2. This includes cessation of the specific testing phase on the third episode of frank aspiration or residue greater than 75% of either vallecular or pyriform housing that is unable to be cleared by the patient with prompting and strategies. Once the study is completed, recordings will be saved and digitally backed up for subsequent analyses of the PAS. Although this study is specifically investigating swallowing safety, this bailout criterion will still allow the study of up to three potential episodes of aspiration so that assessing impact on swallowing safety is still feasible while maintaining patient safety.

Missed Visit 1: When a subject fails to appear for scheduled Visit 1, the site will contact the subject. The site will stress the importance of the evaluation and reschedule within the 28-day window if possible.

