12. CRITERIA FOR INTERVENTION DISCONTINUATION

A subject will be discontinued from the study under the following circumstances:

- If the subject is hemodynamically unstable
- If discontinuation is recommended by treating physician
- At the subject's request

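### The VFSS 1 result decides whether VFSS 2 is done but not whether ROSF is given first, so a subject barred from VFSS 2 could be dosed with no PAS comparison and no set time for most post-dose checks.

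*Protocol*

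**What the plan says.** Protocol Section 10.2.2.1 describes Visit 1. It states "The baseline visit (Day 0, Visit 1) will include a single dose of study drug". After the bolus sequence of the first swallowing study it continues: "Immediately following VFSS 1-PAS, the patient will then be administered ROSF on the dorsum of tongue along the median lingual sulcus". No condition is attached.

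The condition on the VFSS 1 result appears in the next subsection and governs only the second study: "The identical VFSS standardized bolus protocol exam will be performed provided that the subject did not demonstrate frank, gross and observable silent aspiration" in VFSS 1, and the subject's "PAS score in baseline test is 7 or below". The bail-out rule stops further boluses within whichever study is under way; it does not mention the dose.

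Section 12 opens "A subject will be discontinued from the study under the following circumstances" and lists three: haemodynamic instability, a treating physician's recommendation, and the subject's request. No VFSS 1 finding is among them.

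Section 13.5.3 (Power) expects about 20% of recruited subjects to aspirate grossly in VFSS 1 and so not to have VFSS 2, for safety and because of a ceiling effect. It does not say whether they are dosed.

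In Table 3 (Section 10.1), the second vital signs, the brief physical and neurological examinations and the laboratory tests are timed "after VFSS 2 procedure". The second oral examination and adverse event review carry the same anchor through footnote c.

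**The concern.** Read in order, the steps are VFSS 1, dose, then a decision on VFSS 2. The finding that makes a repeat study inadvisable or uninformative is already available when the film is placed, but the text does not use it then.

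Two things follow for a subject who is dosed and then barred. The dose cannot inform the primary outcome, which Section 13.2.1 defines as the within-subject PAS difference, because there is no second score. And most of the scheduled post-dose checks hang on an examination that does not take place, in the subjects whose swallowing was worst at baseline.

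There is also a reporting consequence. SAP 5.1 puts everyone who receives study medication in the safety population, so such a subject would sit in the denominator of the PAS change percentages without being able to appear in the numerator.

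**Working it through.** **1. Is the dose conditional anywhere else?**

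- Eligibility at Visit 1 is reviewed before VFSS 1 (Table 3, Section 10.2.2.1), so it cannot use the result.
- Exclusion 2 (Section 8.1.2) concerns a prior swallowing study. No VFSS is scheduled at screening, so someone never studied passes it. SAP 6.6 partly relaxes this criterion and keeps its scope to prior studies.
- Section 12 lists no VFSS 1 finding.
- Sections 10.2.3, 10.2.4 and 10.3.7 foresee a subject leaving after VFSS 1 and before dosing, but do not link this to the result.

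Nothing in these places withholds the dose from a subject barred from VFSS 2.

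**2. Which checks lose their time point if VFSS 2 is not done?**

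| Check after dosing | Scheduled time | Fallback |
|---|---|---|
| Vital signs | after VFSS 2 | none |
| Brief physical and neurological examinations | after VFSS 2 | none |
| Oral examination | after VFSS 2 | none |
| Scheduled adverse event review | after VFSS 2 | general follow-up only (Sections 10.2.5, 11, 11.2) |
| Laboratory tests | after VFSS 2 | at discontinuation or early termination (Sections 8.2, 10.2.3, 10.2.4; SAP 6.5.4), no clock time |

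The laboratory fallback also depends on treating a barred subject as discontinued, which the protocol does not state.

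**3. The plan's own sample size.** Inputs from the synopsis and Section 13.5.3: effect size 0.6, two-sided alpha 0.05, power 80%, Wilcoxon signed-rank test. With asymptotic relative efficiency 3/π (normal parent), the effective n at 25 is 25 × 3/π = 23.9 and the noncentrality is 0.6 × √23.9 = 2.93. Power is 0.801 and the smallest adequate n is 25, as stated. Subjects barred from VFSS 2 have no second score whether dosed or not, so withholding the dose changes neither the 25 nor the paired analysis.

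**4. How many subjects?** Expected count = 30 × p. The range is the 2.5% to 97.5% binomial quantiles, and P(at least one) = 1 − (1 − p)^30.

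| p | Source | Expected of 30 | 95% range | P(at least one) |
|---|---|---|---|---|
| 0.20 | Section 13.5.3 | 6 | 2 to 11 | 1 − 0.8^30 = 0.999 |
| 0.10 | assumption | 3 | 0 to 7 | 1 − 0.9^30 = 0.958 |
| 0.05 | assumption | 1.5 | 0 to 4 | 1 − 0.95^30 = 0.785 |

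These count subjects barred from VFSS 2. They become counts of subjects dosed without VFSS 2 only if no one stops before dosing.

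**5. Denominator.** SAP 5 bases safety parameters on the safety population, 5.1 defines that as subjects who receive study medication, 6.5 names PAS on the VFSS as safety data, and 6.1.2 rules out imputation. As a hypothetical at the planned size, if all 30 were dosed, 6 had no VFSS 2 and 6 of the other 24 worsened, the rate is 6/24 = 25% among those examined twice but 6/30 = 20% over all dosed.

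**The case against.** The strongest case against this point has four parts.

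*Discretion exists.* The investigator or treating physician may stop a subject after VFSS 1, and Section 10.2.4 covers stopping for any reason. That stands, and it is why the counts above are upper figures. But it is permission, not a rule.

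*Follow-up is not absent.* A reader might infer that a subject dosed without VFSS 2 is left unobserved. The documents do not support that. Section 11 has the investigator monitor every subject, Section 11.2 follows adverse events to resolution where possible even after participation ends, Section 10.2.5 continues follow-up after Visit 1, and SAP 6.5.4 provides laboratory tests at early termination. The gap is confined to the scheduled examinations and the scheduled adverse event review.

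*The dose is not worthless.* A reader might infer that it serves only the PAS comparison. Section 8.3.3 also describes the study as one of tolerability, and Section 13.5.2 plans summaries of adverse events, vital signs, examinations and laboratory results. Section 6.1 makes patients with swallowing difficulty the intended users, so tolerability data in aspirators have some value. Withholding the dose is a trade-off, though a small one.

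*Harm is not shown.* Nothing in the documents says a dissolving film carries a risk like that of repeated barium boluses. This point does not claim it does.

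Two further inferences should be resisted. The 20% refers to gross aspiration, which may not be the same group as PAS 8, so 6 is not a forecast of silent aspirators dosed. And the SAP denominator is not simply undefined: its default reading is all dosed subjects. SAP 6.3.1 already lists subjects who did not complete the VFSS, so only the percentage base needs changing.

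**Conclusion.** The point holds as a gap in the written procedure. As drafted, a subject barred from VFSS 2 by the VFSS 1 result can still be dosed, cannot contribute to the primary comparison, and has no set time for post-dose vital signs, oral and brief examinations or adverse event review.

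At the protocol's own 20%, at most about 6 of the planned 30 would be affected (95% range 2 to 11). Lower assumed rates of 10% and 5% give 3 and 1.5. The true figure may be lower because exclusion 2 removes some known aspirators, although SAP 6.6 loosens it, and because the investigator may withhold the dose.

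The counts apply to the planned 30. A reader might infer that subjects were in fact dosed this way. Nothing in the SAP shows that among the 9 with whom the study closes, and I do not apply the rate to them, because they are counted as completers. Protocol Section 6.4 (Safety) was not available for this check.

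The practical reach is limited by early closure, but the change is cheap and leaves the planned 25 and the paired comparison as they are.

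**What to change.** 1. **Section 10.2.2.1, dosing step.** Give ROSF only if the subject meets the existing conditions for VFSS 2, in that subsection's own wording and as judged live by the investigator straight after VFSS 1. Treat gross aspirators as Section 13.5.3 does: no VFSS 2, hence no dose. List the same criterion in Section 12.
2. **Table 3, footnotes b and c.** Add: *or, if a dosed subject does not have VFSS 2, before leaving the site*. This also covers a subject who is dosed and withdraws before VFSS 2.
3. **SAP 6.5.8.** Base the PAS change percentages on subjects with both VFSS 1 and VFSS 2, and state that number.

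Cost: a sentence, a bullet and a footnote clause in the protocol, and a sentence in the SAP. No visit is added. Barred subjects yield no post-dose adverse event or tolerability data. The decision rests on a live reading that may differ from the later rating, since "recordings will be saved and digitally backed up for subsequent analyses of the PAS" and Section 13.5.1 has them scored by blinded raters afterwards. The existing condition on VFSS 2 already needs such a reading; the change moves it ahead of the dose. Items 1 and 2 can affect only subjects not yet dosed; item 3 can still be applied to the final analysis.
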